10.2. Appendix 2: Clinical Laboratory Tests

The following safety laboratory tests will be performed at times defined in the [SoA](#) section of this protocol. Additional laboratory results may be reported on these samples as a result of the method of analysis or the type of analyzer used by the clinical laboratory, or as derived from calculated values. These additional tests would not require additional collection of blood. Unscheduled clinical laboratory measurements may be obtained at any time during the study to assess any perceived safety issues.

Table 1 Protocol-Required Safety Laboratory Assessments

Hematology	Chemistry	Other	Additional Tests (Needed for Hy's Law)
Hemoglobin	BUN or urea	Ferritin	AST, ALT (repeat)
Hematocrit	Creatinine ^a	hsCRP	Total bilirubin (repeat)
RBC count	Glucose	Procalcitonin	Albumin
Platelet count	Calcium	LDH	Alkaline phosphatase
WBC count	Sodium	CK	(repeat)
Total neutrophils	Potassium	Haptoglobin	Direct bilirubin
(Abs)	Chloride		Indirect bilirubin
Eosinophils (Abs)	Total CO ₂ (bicarbonate)	Thyroid function	Creatine kinase
Monocytes (Abs)	AST, ALT	TSH	GGT
Basophils (Abs)	Total bilirubin	T4 (free)	PT/INR
Lymphocytes (Abs)	Alkaline phosphatase		Total bile acids
	Albumin	Coagulation	Acetaminophen drug
	Total protein	PT/aPTT	and/or protein adduct
		Fibrinogen	levels
		D-dimer	
		SARS-CoV-2 serology (IgM, IgG)	
		FSH ^b	
		Pregnancy test (β-hCG) ^c	

- a. eGFR will be calculated using the method developed by the CKD-EPI using serum creatinine. ²⁸
- b. FSH testing is performed locally for confirmation of postmenopausal status only.
- c. Local urine testing will be standard for the protocol unless serum testing is required by local regulation or IRB/EC. Serum or urine β-hCG for female participants of childbearing potential.

The investigator must review the laboratory report, document this review, and record any clinically relevant changes occurring during the study in the AE section of the CRF.

10.3. Appendix 3: Adverse Events: Definitions and Procedures for Recording, Evaluating, Follow-Up, and Reporting

10.3.1. Definition of AE

AE Definition

• An AE is any untoward medical occurrence in a patient or clinical study participant, temporally associated with the use of study intervention, whether or not considered related to the study intervention.• Note: An AE can therefore be any unfavorable and unintended sign (including an abnormal laboratory finding), symptom, or disease (new or exacerbated) temporally associated with the use of study intervention.

Events Meeting the AE Definition

• Any abnormal laboratory test results (hematology, clinical chemistry, or urinalysis) or other safety assessments (eg, ECG, radiological scans, vital sign measurements), including those that worsen from baseline, considered clinically significant in the medical and scientific judgment of the investigator. Any abnormal laboratory test results that meet any of the conditions below must be recorded as an AE:
• Is associated with accompanying symptoms.• Requires additional diagnostic testing or medical/surgical intervention.• Leads to a change in study dosing (outside of any protocol-specified dose adjustments) or discontinuation from the study, significant additional concomitant drug treatment, or other therapy.• Exacerbation of a chronic or intermittent preexisting condition, including either an increase in frequency and/or intensity of the condition.• New condition detected or diagnosed after study intervention administration, even though it may have been present before the start of the study.• Signs, symptoms, or the clinical sequelae of a suspected drug-drug interaction.• Signs, symptoms, or the clinical sequelae of a suspected overdose of either study intervention or a concomitant medication. Overdose per se will not be reported as an AE or SAE unless it is an intentional overdose taken with possible suicidal/self-harming intent. Such overdoses should be reported regardless of sequelae.

Events **NOT** Meeting the AE Definition

- Any clinically significant abnormal laboratory findings or other abnormal safety assessments that are associated with the underlying disease, unless judged by the investigator to be more severe than expected for the participant's condition.
- The disease/disorder being studied or expected progression, signs, or symptoms of the disease/disorder being studied, unless more severe than expected for the participant's condition.
- Medical or surgical procedure (eg, endoscopy, appendectomy): the condition that leads to the procedure is the AE.
- Situations in which an untoward medical occurrence did not occur (social and/or convenience admission to a hospital).
- Anticipated day-to-day fluctuations of preexisting disease(s) or condition(s) present or detected at the start of the study that do not worsen.

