Note: "Enrolled" means a participant's, or his or her legally authorized representative's, agreement to participate in a clinical study following completion of the informed consent process and screening. A participant will be considered enrolled if the informed consent is not withdrawn prior to participating in any study activity after screening. Potential participants who are screened for the purpose of determining eligibility for the study, but do not participate in the study, are not considered enrolled, unless otherwise specified by the protocol.

Intervention Groups and Duration

Participants will be screened within 48 hours before randomization. Eligible participants will receive PF-07321332 plus ritonavir or placebo orally q12h for 5 days. The total study duration is up to 24 weeks, with study intervention through Day 5 or Day 6, efficacy assessments through Day 28, a safety follow-up period through Day 34, and long-term follow-up at Weeks 12 and 24.

Data Monitoring Committee or Other Independent Oversight Committee: Yes

An independent E-DMC will review unblinded data to ensure the safety of participants throughout the duration of the study, as specified in the E-DMC Charter. In addition to up to weekly reviews of safety, the E-DMC will review the following:

- Sentinel cohort safety review: The E-DMC will review unblinded safety data after approximately the first 100 randomized participants have completed through Day 10. Whether enrollment is paused for this review will depend on the successful completion of the Study C4671005 sentinel cohort (after approximately the first 60 randomized participants have completed through Day 10). If the C4671005 sentinel cohort safety review has successfully completed and no clinically significant safety signals have been identified prior to enrollment of the first 100 participants in this Study C4671002, the study will continue without pause. Otherwise, enrollment of Study C4671002 will be paused pending the E-DMC review of safety data. After review of the sentinel cohort in this Study C4671002, the frequency of safety reviews may be reduced subsequently based on E-DMC recommendations.
- Proof-of-concept assessment: Viral load data when 25% (approximately 200 participants in the primary analysis set with evaluable data) complete the Day 5 assessments. Enrollment will not be paused during review of these data, but may be paused or stopped following E-DMC review.

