8.3.1. Time Period and Frequency for Collecting AE and SAE Information

The time period for actively eliciting and collecting AEs and SAEs (“active collection period”) for each participant begins from the time the participant provides informed consent, which is obtained before the participant’s participation in the study (ie, before undergoing any study-related procedure and/or receiving study intervention), through and including a minimum of 28 calendar days, except as indicated below, after the last administration of the study intervention.

Follow-up by the investigator continues throughout and after the active collection period and until the AE or SAE or its sequelae resolve or stabilize at a level acceptable to the investigator.

For participants who are screen failures, the active collection period ends when screen failure status is determined.

If the participant withdraws from the study and also withdraws consent for the collection of future information, the active collection period ends when consent is withdrawn.

If a participant permanently discontinues or temporarily discontinues study intervention because of an AE or SAE, the AE or SAE must be recorded on the CRF and the SAE reported using the CT SAE Report Form.

After the defined active collection period, participants are contacted by phone for a vital status check at Week 12 and Week 24 (long-term follow-up period). Any SAE identified during this follow-up period and determined to be related to PF-07321332/ritonavir is reported to Pfizer Safety on the CT SAE Report Form immediately upon awareness and under no circumstance should this exceed 24 hours, as indicated in [Appendix 3](#). Investigators are not otherwise obligated to report AEs after the defined active collection period.

Investigators are not obligated to actively seek information on AEs or SAEs after the participant has concluded study participation. However, if the investigator learns of any SAE, including a death, at any time after a participant has completed the study, and he/she considers the event to be reasonably related to the study intervention, the investigator must promptly report the SAE to Pfizer using the CT SAE Report Form.

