- For each AE or SAE, the investigator **must** document in the medical notes that he/she has reviewed the AE or SAE and has provided an assessment of causality.
- There may be situations in which an SAE has occurred and the investigator has minimal information to include in the initial report to the sponsor. However, **it is very important that the investigator always make an assessment of causality for every event before the initial transmission of the SAE data to the sponsor.**
- The investigator may change his/her opinion of causality in light of follow-up information and send an SAE follow-up report with the updated causality assessment.
- The causality assessment is one of the criteria used when determining regulatory reporting requirements.
- If the investigator does not know whether or not the study intervention caused the event, then the event will be handled as “related to study intervention” for reporting purposes, as defined by the sponsor. In addition, if the investigator determines that an SAE is associated with study procedures, the investigator must record this causal relationship in the source documents and CRF, and report such an assessment in the dedicated section of the CT SAE Report Form and in accordance with the SAE reporting requirements.

Follow-Up of AEs and SAEs

- The investigator is obligated to perform or arrange for the conduct of supplemental measurements and/or evaluations, as medically indicated or as requested by the sponsor, to elucidate the nature and/or causality of the AE or SAE as fully as possible. This may include additional laboratory tests or investigations, histopathological examinations, or consultation with other healthcare providers.
- If a participant dies during participation in the study or during a recognized follow-up period, the investigator will provide Pfizer Safety with a copy of any postmortem findings, including histopathology.
- New or updated information will be recorded in the originally submitted documents.
- The investigator will submit any updated SAE data to the sponsor within 24 hours of receipt of the information.

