3.6.1. Adverse Events

An adverse event (AE) is any untoward medical occurrence in a study participant administered a product or medical device; the event need not necessarily have a causal relationship with the treatment or usage. An adverse event is considered a

Treatment-Emergent Adverse Event (TEAE) if the event started on or after the study medication start date and time.

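### SAP 3.6.1 defines a TEAE by start date and time alone, so an AE with a recorded pre-dose onset that worsens on study drug under the same record is not counted

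*Protocol*

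**What the plan says.** **What counts as an AE.** Protocol 10.3.1 covers any unfavourable sign, "symptom, or disease (new or exacerbated) temporally associated with the use of study intervention". Its list of qualifying events includes "Exacerbation of a chronic or intermittent preexisting condition, including either an increase in frequency and/or intensity of the condition". It also includes clinically significant laboratory or vital-sign findings that have deteriorated since baseline, and a "New condition detected or diagnosed after study intervention administration, even though it may have been present before the start of the study". Signs and symptoms of the disease under study are excluded unless they are more severe than expected for that participant.

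**When collection starts.** Under Protocol 8.3.1 the active collection period "begins from the time the participant provides informed consent". The Synopsis gives the length of the pre-randomisation interval: "Participants will be screened within 48 hours before randomization".

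**What counts as treatment-emergent.** Under SAP 3.6.1 an AE is a "Treatment-Emergent Adverse Event (TEAE) if the event started on or after the study medication start date and time". SAP 6.6.1 adds an upper limit at Day 34, again by start date.

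**Where the rule is used.** Incidence of TEAEs is a secondary endpoint (Protocol Section 3, SAP 3.2). It is tabulated by system organ class and preferred term in SAP 6.2.1, and by vaccination status in SAP 6.6.2.

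**How an AE is updated.** Protocol 10.3.3 says that "New or updated information will be recorded in the originally submitted documents". Neither document says whether a worsening opens a new AE record or takes a new onset date.

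**The concern.** The AE definition recognises two kinds of event: something new, and something already present that gets worse. The treatment-emergent definition recognises only the first, through the recorded start. An event can therefore be a valid AE under the protocol, deteriorate on study drug, and still be missing from the main tolerability table because its record opened before the first dose.

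Pre-dose records can arise by design. Collection begins at consent, baseline laboratory samples are drawn before dosing (Schedule of Activities), and vital signs are taken at screening and baseline. A clinically significant laboratory abnormality, a raised blood pressure or another non-COVID event could each be entered as an AE before the first dose. Hypertension is a listed potential risk of PF-07321332 (Protocol 2.3.1) and one of the special-interest terms in SAP Appendix 5, so worsening of an existing blood-pressure AE is a form of harm this trial would want to see. If the drug causes such worsening, the omitted events fall more heavily in the active arm and the tolerability difference is understated.

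**Working it through.** The plan gives no figure to reproduce on this point. The check is textual: apply the SAP 3.6.1 rule to each type of record that the protocol allows.

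1. **AE starts on or after first dose.** The start is post-dose, so it is a TEAE and is counted.
2. **Condition in the medical history worsens on drug, and the exacerbation is entered as its own AE.** Its start is the date of worsening, which is post-dose. It is counted.
3. **AE starts between consent and first dose, then worsens on drug under the same record.** The start is pre-dose. It is not a TEAE, whatever grade it reaches.
4. **Condition first detected after dosing, but dated by the investigator to before it.** It is an AE under Protocol 10.3.1. The recorded start is pre-dose, so it is not a TEAE, and later worsening under that record does not change this.

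Cases 3 and 4 are the gap. The other SAP sections that use AEs or TEAEs (3.2, 3.6, 6.2.1, 6.2.2, 6.6, 6.6.1, 6.6.2) contain no worsening clause that would bring them back.

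**Form of the effect on the arm comparison.** For case 3, let *p* be the proportion of participants whose only route into the TEAE table is an AE with pre-dose onset. Let *w*(active) and *w*(placebo) be the probabilities that this event worsens after dosing under the same record. Pre-dose onset cannot depend on treatment, so *p* is the same in both arms in expectation. Then

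- TEAE incidence missed in an arm = *p* × *w*(arm)
- understatement of the active-minus-placebo difference = *p* × [*w*(active) − *w*(placebo)], which cannot exceed *p*.

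The documents give none of *p*, *w*(active) or *w*(placebo), so no number follows. What they do say suggests that *p* is small. The interval before randomisation is at most 48 hours, and the Schedule of Activities notes that screening can often be finished in under 24 hours, with randomisation and first dose possible on the same calendar day. The exclusion of expected COVID-19 symptoms also removes the complaints most likely to be present at that time.

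**The case against.** The strongest reply is that the two definitions mostly agree. Protocol 10.3.1 makes the exacerbation itself the AE, and an exacerbation on drug begins on drug. Entered that way it is a TEAE already. This stands, and it confines the problem to cases 3 and 4.

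A reader might infer something larger: that gastrointestinal complaints or fatigue present at entry and aggravated by ritonavir are systematically lost. The documents do not support that. These complaints are listed COVID-19 symptoms (Protocol Appendix 9) and are not AEs unless more severe than expected. If one crosses that threshold after dosing, it first qualifies as an AE then, and the natural start date is post-dose.

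A reader might also take the 10.3.3 sentence on updates as fixing the original onset date. It does not. It is a general follow-up instruction placed among bullets on post-mortem findings and SAE updates, and it says nothing about onset dates or new records. Recording conventions may lie in the CRF Completion Requirements (Protocol 10.1.7), and a worsening rule may lie in the CDISC and Pfizer standards cited in SAP 3.6 and 6.6. Neither is reproduced, so neither can be relied on to override an explicit definition in SAP 3.6.1.

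Other outputs recover part of the harm. SAP 6.2.2 summarises SAEs and AEs leading to discontinuation without a TEAE restriction. SAP 6.2.7 and 6.2.10 compare the arms on severe and worsening targeted symptoms. SAP 6.6.3 gives shift tables for selected laboratory tests, and SAP 5.2 lists individual AEs. What remains uncovered in the incidence comparison is mainly non-serious worsening, without discontinuation, of an AE that already had a pre-dose record.

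**Conclusion.** The gap is real and minor. SAP 3.6.1 states a rule that misclassifies some on-drug worsening, and nothing else in the SAP corrects it. It affects AEs with a recorded onset before first dose whose worsening stays under the same record.

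The size is unknown. Any count of affected participants would rest on invented rates for pre-dose AEs and for their worsening, and none should be quoted. The conclusion that the effect is small rests on the short consent-to-dose interval, the exclusion of expected disease symptoms, and sites entering many exacerbations as new events. The last of these is not stated in the documents. The direction is clearer: if the drug worsens such events more often than placebo does, the present definition understates the difference.

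This is not a general conflict between the protocol's AE definition and the SAP, because exacerbations with their own on-drug start date are counted.

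**What to change.** In SAP 3.6.1, define a TEAE as an AE that either

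- starts on or after the first dose date and time, or
- has an earlier onset and increases in DAIDS grade, or becomes serious, on or after the first dose date and time.

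Add a default for incomplete records. Where the record does not show when the grade rose, count a pre-dose-onset AE still ongoing after first dose as treatment-emergent if its recorded grade exceeds its pre-dose grade, or if its pre-dose grade is unknown. The second part of the default also covers conditions detected after dosing but dated to before it.

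AEs are already graded on the DAIDS scale under Protocol 10.3.3, so the rule can be programmed on existing records for every participant. A change to CRF recording is not advised at this stage: with three interim analyses complete, it would make AE records before and after the change differ.

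The cost is a few lines in the SAP and a small programming change. TEAE counts may rise slightly in both arms, and the default for unknown grades will bring in some events that did not truly worsen. If the third interim analysis used the present definition, final and interim TEAE counts may differ slightly, and a footnote should say why.

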10.3.2. Definition of an SAE

An SAE is defined as any untoward medical occurrence that, at any dose, meets one or more of the criteria listed below:

a. Results in death

b. Is life-threatening

The term "life-threatening" in the definition of "serious" refers to an event in which the participant was at risk of death at the time of the event. It does not refer to an event that hypothetically might have caused death if it were more severe.

c. Requires inpatient hospitalization or prolongation of existing hospitalization

In general, hospitalization signifies that the participant has been admitted (usually involving at least an overnight stay) at the hospital or emergency ward for observation and/or treatment that would not have been appropriate in the physician's office or outpatient setting. Complications that occur during hospitalization are AEs. If a complication prolongs hospitalization or fulfills any other serious criteria, the event is serious. When in doubt as to whether "hospitalization" occurred or was necessary, the AE should be considered serious.

Hospitalization for elective treatment of a preexisting condition that did not worsen from baseline is not considered an AE.

d. Results in persistent or significant disability/incapacity
 
• The term disability means a substantial disruption of a person’s ability to conduct normal life functions.• This definition is not intended to include experiences of relatively minor medical significance, such as uncomplicated headache, nausea, vomiting, diarrhea, influenza, and accidental trauma (eg, sprained ankle), that may interfere with or prevent everyday life functions but do not constitute a substantial disruption.

e. Is a congenital anomaly/birth defect

f. Is a suspected transmission via a Pfizer product of an infectious agent, pathogenic or non-pathogenic, is considered serious.
 
The event may be suspected from clinical symptoms or laboratory findings indicating an infection in a participant exposed to a Pfizer product. The terms “suspected transmission” and “transmission” are considered synonymous. These cases are considered unexpected and handled as serious expedited cases by pharmacovigilance personnel. Such cases are also considered for reporting as product defects, if appropriate.


g. Other situations:
 
• Medical or scientific judgment should be exercised by the investigator in deciding whether SAE reporting is appropriate in other situations, such as significant medical events that may jeopardize the participant or may require medical or surgical intervention to prevent one of the other outcomes listed in the above definition. These events should usually be considered serious.• Examples of such events include invasive or malignant cancers, intensive treatment in an emergency room or at home for allergic bronchospasm, blood dyscrasias or convulsions that do not result in hospitalization, or development of drug dependency or drug abuse.

